## 5.3 Inclusion and Exclusion Criteria

Inclusion criteria:

(1) Being a current healthcare professional (2) Aged between 18 and 70 years (3) Ability to understand Spanish (4) Digital literacy and access to a smartphone, tablet, or computer with internet access (5) Continuity in the same workplace for at least 6 months (6) Signing the informed consent form

Exclusion criteria: (1) Diagnosis of severe mental illness (2) Suicidal ideation (3) Substance abuse or related disorders

## 5.4 Variables and Measures

Main variables (implementation): In line with the Consolidated Framework for Implementation Research (CFIR), Proctor et al. (2011), and Hermes et al. (2019), this study will evaluate the following implementation outcomes: feasibility, acceptability, and sustainability. Additionally, focus groups will be conducted with key stakeholders at each center after the intervention (post-treatment) to qualitatively assess implementation domains.

Feasibility:

Defined as the extent to which a new treatment can be successfully used or carried out in a specific setting. Feasibility will be assessed through passive data collected by the online platform, such as frequency of use. The Feasibility of Intervention Measure (FIM) (Weiner et al., 2017), consisting of 4 items, will also be used. This scale has shown good psychometric properties with high internal consistency ( $\alpha = 0.85-0.91$ ) and test-retest reliability coefficients ( $r = 0.73-0.88$ ).

Acceptability:

Defined as the perception among stakeholders that the intervention is satisfactory or useful. It will be assessed using:

- System Usability Scale (SUS) (Bangor et al., 2008): A 10-item questionnaire measuring usability, qualitatively linked to intervention quality and acceptability. The Spanish version has demonstrated good internal consistency ( $\alpha = 0.81$ )

(Sevilla-González et al., 2020). - Internet-based Client Satisfaction Questionnaire (CSQ-I) (Boß et al., 2016): An 8-item, 4-point Likert scale questionnaire measuring overall satisfaction.

**Sustainability:**

Assessed through ongoing monitoring of platform usage (access and participation logs) and semi-structured interviews to determine the integration of the program into users' daily routines.

**Secondary variables (clinical):** - Perceived Stress Scale (PSS) (Cohen et al., 1983): 10 items rated on a 5-point Likert scale assessing unpredictability, uncontrollability, and overload during the past month. Scores range from 0 to 40, with higher scores indicating higher perceived stress. The Spanish version has good psychometric properties ( $\alpha = 0.81$ ; test-retest reliability  $r = 0.77$ ). - Patient Health Questionnaire-9 (PHQ-9) (Kroenke et al., 2001): 9-item self-report scale assessing severity of depressive symptoms. The Spanish version demonstrates comparable diagnostic validity with 88% sensitivity and specificity. - Generalized Anxiety Disorder-7 (GAD-7) (Spitzer et al., 2006): 7-item self-report scale assessing anxiety over the past two weeks. Total scores range from 0 to 21; higher scores indicate more severe symptoms. The Spanish version has shown good psychometric properties (García-Campayo et al., 2010).

### **5.5 Sample Size**

For the pilot study, a sensitivity analysis was conducted using a paired samples t-test, assuming a moderate effect size (Cohen's  $dz = 0.46$ ), 95% confidence level ( $\alpha = 0.05$ ), and 80% statistical power. The required sample size was determined to be  $N = 30$ . For the full study, the same analysis was applied with a smaller effect size (Cohen's  $dz = 0.25$ ), resulting in a required sample size of  $N = 100$ .

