### **3. Hypotheses**

1. Primary hypothesis (implementation): Implementing the MINDxYOU program in healthcare settings will be feasible, acceptable, and sustainable among healthcare professionals.
2. Secondary hypothesis (clinical effectiveness): Participants using the program will experience a significant reduction in perceived stress, anxiety, and depressive symptoms compared to baseline.
3. Adherence hypothesis: Program usage and participant satisfaction will be positively associated with perceived ease of use and perceived effectiveness of the intervention.
4. Barriers and facilitators hypothesis: Factors such as work overload and lack of time may hinder program adoption, while accessibility and the flexibility of the online format will facilitate its integration into the routines of healthcare professionals.

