### **4. Objectives**

Primary Objective:

To evaluate the feasibility, acceptability, and sustainability of implementing the MINDxYOU program in real-world healthcare settings.

Secondary Objective:

To assess clinical outcomes of the intervention, including its effects on perceived stress, anxiety levels, and depression symptoms among healthcare professionals.

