## 6. Data Analysis

For the implementation analysis, outcomes will be assessed following the framework by Hermes et al. (2019) and Proctor et al. (2011). Passive data will include objective usage metrics (e.g., logins, frequency of use, completed modules, tasks submitted). Quantitative data from questionnaires will be analyzed using appropriate statistical methods, while qualitative data will be gathered through stakeholder interviews.

For the clinical analysis, variables will be described using mean and 95% confidence intervals for normally distributed quantitative variables, or medians and interquartile range for non-normally distributed data. Effectiveness variables (stress, anxiety, and depression) will be compared using paired-samples t-tests.

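### The sample sizes of 30 and 100 give 80% power only under a one-sided test that the protocol never declares; two-sided at 0.05 the power is 68% and 70%

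*Protocol*

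**What the plan says.** Section 5.5 of the protocol sizes both phases. For the pilot, "a sensitivity analysis was conducted using a paired samples t-test, assuming a moderate effect size", with dz = 0.46. The error rate is given as a "95% confidence level" with alpha = 0.05. The text continues "and 80% statistical power. The required sample size was determined to be" 30. Then: "For the full study, the same analysis was applied with a smaller effect size", dz = 0.25, which leads to 100. The paragraph does not say whether the test is one- or two-sided.

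Three other sections bear on the direction of the test:

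- Section 3 words the clinical hypothesis as a "significant reduction in perceived stress, anxiety, and depressive symptoms compared to baseline". This is directional, but no one-sided test is named.
- Section 4 words the secondary objective without a direction: "To assess clinical outcomes of the intervention, including its effects on perceived stress, anxiety levels, and depression symptoms among healthcare professionals".
- Section 6 plans the analysis as follows: "Effectiveness variables (stress, anxiety, and depression) will be compared using paired-samples t-tests". No direction is given.

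**The concern.** A paired t-test calculation is fixed by alpha, sidedness, power, effect size and N. Section 5.5 gives all of these except sidedness, and its figures do not hold under the usual two-sided default. A reader who takes alpha = 0.05 and an unqualified paired t-test at face value will believe the study has 80% power when it has about 70%.

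The paragraph also describes its calculation in two incompatible ways. A sensitivity analysis fixes N and solves for the detectable effect; a required sample size fixes the effect and solves for N.

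What is at stake is the only stated basis for 30 and 100 participants, and the power of the stress, anxiety and depression comparisons. The primary outcomes (feasibility, acceptability, sustainability) do not rest on these tests. If sidedness is left open until the data are in, it can also be chosen after the results are known, which matters in a before-after design without a control group.

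**Working it through.** **Inputs (all from section 5.5).** Paired t-test; alpha = 0.05; power 80%; dz = 0.46 with N = 30; dz = 0.25 with N = 100. Sidedness is not stated, so both versions are run.

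**Formula.** With N pairs, the test statistic has df = N − 1 and noncentrality dz × √N. One-sided power is P(T > t[0.95, df]). Two-sided power is P(|T| > t[0.975, df]). T follows the noncentral t distribution.

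Noncentrality: pilot 0.46 × √30 = 2.520; full study 0.25 × √100 = 2.500.

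**Step 1: reproduce the plan's figures, one-sided 0.05.**

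| | Critical t | Power at stated N and dz | dz detectable with 80% power |
|---|---|---|---|
| N = 30, dz = 0.46 | 1.699 | 79.3% | 0.465 |
| N = 100, dz = 0.25 | 1.660 | 79.9% | 0.250 |

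To four decimals the detectable effects are 0.4649 and 0.2504, which round to the protocol's 0.46 and 0.25. Both pairs therefore match a one-sided calculation of the detectable effect at a fixed N. Solving for N from the rounded effects gives 31 and 101. That one-participant difference comes from rounding dz and carries no weight.

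**Step 2: the same inputs, two-sided 0.05.**

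| | Critical t | Power at stated N and dz | N for 80% power | dz detectable with 80% power |
|---|---|---|---|---|
| N = 30, dz = 0.46 | 2.045 | 68.3% | 40 (39 gives 79.9%) | 0.529 |
| N = 100, dz = 0.25 | 1.984 | 69.7% | 128 (127 gives 79.8%) | 0.283 |

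The shortfall is 40 − 30 = 10 pairs and 128 − 100 = 28 pairs. The type II error is 100 − 68.3 = 31.7% and 100 − 69.7 = 30.3%, against the 20% implied.

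**Step 3: does a cruder formula rescue the two-sided reading?** The normal approximation is N = ((z for alpha + z for power) / dz)².

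- Two-sided: ((1.960 + 0.842) / 0.46)² gives 38 after rounding up, and ((1.960 + 0.842) / 0.25)² gives 126.
- One-sided, with 1.645 in place of 1.960: 30 and 99.

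The approximation also fits only one-sided.

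**Step 4: implied alpha.** The two-sided alpha at which the stated N and dz give exactly 80% power is 0.105 for the pilot and 0.101 for the full study, about twice the stated 0.05. This restates the one-sided result and is not separate evidence.

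**The case against.** The strongest reply is that nothing has been miscalculated. Section 5.5 never says two-sided, the figures are right for a one-sided test at 0.05, and the hypothesis in section 3 predicts a reduction, so a one-sided calculation is natural. The stated 95% confidence level is only alpha = 0.05 in other words and does not settle the matter. An SAP that is not at hand may declare one-sided tests. The tests are secondary, and no success criterion or move between phases depends on them.

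Much of this stands. The fault is best described as an undeclared assumption, and its reach is limited to the sample-size justification and the secondary outcomes. A directional hypothesis, however, does not declare a one-sided test: such hypotheses are routinely tested two-sided. A later SAP cannot fully repair the paragraph either. If it specifies two-sided tests, the 80% in section 5.5 is wrong; if it specifies one-sided tests, section 5.5 still omits the assumption on which its figures depend. The protocol itself states the power, so it should state what that power requires.

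It is also fair to say that quoting dz = 0.53 and 0.28 makes the paragraph consistent without showing that such effects are plausible. Section 5.5 gives no basis for 0.46 and 0.25 either.

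**Conclusion.** The concern holds. The 80% power claimed for N = 30 at dz = 0.46 and N = 100 at dz = 0.25 is correct only for one-sided testing at 0.05, which the protocol does not declare. If the section 6 tests are run two-sided at 0.05, power is 68% and 70%, and 80% would need 40 and 128 pairs. The mismatch between a sensitivity analysis and a required sample size is real whichever side is chosen, but on its own it is a matter of wording.

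The figures assume that every enrolled participant supplies a complete pair, that each outcome is tested separately at 0.05, and that the exact t-test applies. This should be corrected; it does not threaten the primary implementation objective.

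**What to change.** Choose one of two courses, and write it into sections 5.5 and 6 before the outcome data are analysed.

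1. **Two-sided (preferred).** Keep 30 and 100. State that, for a two-sided paired t-test at alpha 0.05, 30 complete pairs give 80% power for dz = 0.53 (68% for dz = 0.46), and 100 complete pairs give 80% power for dz = 0.28 (70% for dz = 0.25). Name the test as two-sided in section 6.
2. **One-sided.** Declare one-sided testing at 0.05 in both sections, and justify it with reference to the directional hypothesis in section 3.

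In either case, describe the figures as effects detectable at a fixed N and remove the statement that these numbers are required.

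The cost is wording only, with no extra participants. Under the first course the stated detectable effects become somewhat larger; under the second the one-sided choice has to be defended.

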### **5. Methodology**

#### **5.1 Study Design**

This study will adopt a Hybrid Type III effectiveness-implementation design, which combines the evaluation of implementation processes with the observation of the clinical outcomes of the intervention. This type of design primarily focuses on implementation strategies (feasibility, acceptability, and sustainability), while clinical outcomes are assessed in a naturalistic way without randomization at the patient level (Proctor et al., 2011).

Study phases:

- Phase 1 – Pilot study (N=30): An initial pilot study will be conducted at the Regional University Hospital of Málaga with a group of healthcare professionals. The program's acceptability will be assessed through surveys and interviews, and its use within the clinical setting will be observed.
- Phase 2 – Expanded study (N=100): In this phase, the program will be implemented at scale within the Andalusian Health Service (SAS), including a broader sample of healthcare professionals from hospitals and primary care centers.

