## 7. Ethics and Dissemination

All procedures will follow the Declaration of Helsinki (1964 and subsequent amendments; latest version adopted at the 64th WMA General Assembly, Fortaleza, Brazil). Signed informed consent will be obtained from all participants, who will not receive any financial compensation. Participants will be informed about study procedures, potential risks, and their right to withdraw at any time.

Major protocol modifications (e.g., changes in eligibility, outcomes, analysis) must be approved by ethics committees. Data confidentiality will comply with Spanish Organic Law 3/2018 on Data Protection and Digital Rights, aligned with the EU GDPR. A specific plan will be implemented to ensure maximum data security, using two separate systems and databases: one for personal data and one for clinical data, hosted on separate servers.

Study results will be published in peer-reviewed biomedical journals and presented at national and international conferences. Reporting will adhere to the StaRI (Standards for Reporting Implementation Studies) statement (Pinnock et al., 2017).

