## 10. Study Limitations and Strengths

This study's strengths include its innovative implementation focus, accessible online format, evidence-based design, and applicability across various healthcare environments. However, limitations include possible low adherence, lack of a control group, variability in participation, and dependence on technology. Its potential integration into the public health system makes it a valuable resource for supporting healthcare workers' mental health, reducing demand on mental health services, and improving patient care quality.

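### Section 5.5 derives 30 and 100 as the complete pairs needed for 80% power, and the same numbers are the phase sizes, so the stated power holds only with essentially complete follow-up

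*Protocol*

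**What the plan says.** Section 5.5 (Sample Size) reports that "a sensitivity analysis was conducted using a paired samples t-test", with dz 0.46, a "95% confidence level" (alpha 0.05) and "80% statistical power", giving 30 for the pilot. The same method with dz 0.25 is described as "resulting in a required sample size of $N = 100". The section does not say whether the test is one- or two-sided, and it mentions neither retention nor attrition.

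Section 5.1 (Study Design) uses the same numbers for the size of each phase, for example "Phase 2 – Expanded study (N=100", and so does the Abstract. Neither says whether these are participants enrolled or participants with complete data.

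Section 6 (Data Analysis) states that stress, anxiety and depression "will be compared using paired-samples t-tests".

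On possible loss, section 7 tells participants of "their right to withdraw at any time", and section 10 says that "limitations include possible low adherence, lack of a control group, variability in participation". Section 5.7 describes a self-guided online programme of about 8 weeks. Section 5.6 plans assessments of all study variables every 8 weeks and has no rule on replacing participants, either way.

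**The concern.** A paired t-test uses only participants who have both scores. If 30 and 100 are the numbers enrolled, every missing follow-up takes the analysis below the number that section 5.5 calls required. The protocol names withdrawal, possible low adherence and variable participation, but none of these enters the sample size.

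At stake is the stated power for the secondary hypothesis in section 3, a reduction in stress, anxiety and depressive symptoms from baseline. If follow-up is incomplete, a non-significant result would come from a comparison with less power than the protocol states. The calculation in 5.5 is also the only justification given for either N.

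**Working it through.** **Inputs.** From section 5.5: paired t-test, alpha 0.05, power 80%, dz 0.46 with N = 30, dz 0.25 with N = 100. Sidedness is not stated, so both readings are tried. Retention is not given anywhere, so it is an assumption shown over a range.

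**Step 1: reproduce the plan's figures.** The normal approximation is n = ((z_alpha + z_power)/dz)², with z_power = 0.842.

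- One-sided (z_alpha = 1.645): (2.487/0.46)² = 29.2, so 30; (2.487/0.25)² = 98.9, so 99.
- Two-sided (z_alpha = 1.960): (2.802/0.46)² = 37.1, so 38; (2.802/0.25)² = 125.6, so 126.

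The exact calculation uses the noncentral t with n − 1 degrees of freedom and noncentrality dz·√n. It gives 31 and 101 one-sided, 40 and 128 two-sided. The stated 30 and 100 therefore match a one-sided alpha of 0.05 and do not match a two-sided one.

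**Step 2: power with every pair complete.**

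- N = 30, dz 0.46: noncentrality 0.46·√30 = 2.52; power 79.3% one-sided, 68.3% two-sided.
- N = 100, dz 0.25: noncentrality 0.25·√100 = 2.50; power 79.9% one-sided, 69.7% two-sided.

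Even on the favourable reading there is no margin above 80%.

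**Step 3: power when some pairs are missing.** The number of pairs is N × retention, and everything else is unchanged. The retention values are assumed.

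| Retention | Phase 1 pairs | Phase 1 power, one-sided | Phase 2 pairs | Phase 2 power, one-sided |
|---|---|---|---|---|
| 100% | 30 | 79.3% | 100 | 79.9% |
| 90% | 27 | 75.3% | 90 | 76.1% |
| 80% | 24 | 70.6% | 80 | 71.6% |
| 70% | 21 | 65.2% | 70 | 66.5% |

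For small losses, one missing pair gives 78.0% in Phase 1 (29 pairs) and 79.5% in Phase 2 (99 pairs). Five missing pairs in Phase 2 (95 left) give 78.1%.

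**Step 4: the effect detectable with 80% power.** With 70 pairs in Phase 2, the dz that gives 80% power one-sided is 0.30, against the 0.25 in the plan.

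**The case against.** Several stronger readings are tempting, and the protocol does not support them.

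- *Any withdrawal puts 80% power out of reach.* On a two-sided test, 80% is missed with nobody lost (68.3% and 69.7%), so withdrawal is not the cause there. On a one-sided test Phase 2 falls slowly and still has 78.1% with five pairs missing. Only the pilot is sensitive to one or two losses.
- *The protocol expects low adherence and so contradicts itself.* Section 10 calls low adherence possible and gives no rate, and a right to withdraw is standard ethics wording. An allowance is absent; no statement is contradicted.
- *Low adherence means lost pairs.* Section 5.6 assesses participants every 8 weeks without making this depend on module completion; only the usability scale is tied to modules. Someone who stops the modules but answers the questionnaire still contributes a pair.
- *Participants will not be replaced.* The protocol is silent on this. It also sets no recruitment cap, so recruiting until 100 pairs are complete would be consistent with the text.

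A sponsor could add that the powered outcomes are secondary in a Hybrid Type III design, and that 5.5 speaks of a sensitivity analysis, so the sizes may have been fixed first. With 30 pairs the one-sided detectable dz is 0.465, close to the stated 0.46. These points limit the weight of the concern. They do not remove it: 5.5 also calls the sizes required, attaches 80% power to them, and leaves unsaid how many complete pairs are expected. Nor is this a missing-data method that could be left to a later analysis plan, because the sample size justification stands in the protocol.

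**Conclusion.** The concern holds in a limited form. Section 5.5 attaches 80% power to numbers of complete pairs that are also the phase sizes, with no allowance for missing follow-up. If 30 and 100 are numbers enrolled, the 80% holds only with essentially complete follow-up and a one-sided test. Taking the one-sided reading, an assumed 10% loss costs about 4 percentage points in each phase, and an assumed 20% loss about 8 to 9. The shortfall of about 11 points (Phase 1) and 10 points (Phase 2) on a two-sided test at full retention belongs to the separate question of sidedness and should not be counted as attrition.

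The size rests on retention values that the protocol does not supply, and on reading the phase sizes as enrolment, which it does not state. The consequence is confined to the secondary clinical hypothesis; the feasibility, acceptability and sustainability outcomes are not touched. A correction is worth making because it changes a stated figure at almost no cost.

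**What to change.** In section 5.5, say whether 30 and 100 are numbers enrolled or numbers of complete pairs. If they are numbers enrolled, state the assumed retention and restate the power, or the dz detectable with 80% power, for the expected number of complete pairs. A short table over a range of retention would do. Update the Phase 2 figure with the pilot's observed retention before Phase 2 opens. The restated figures should name the sidedness used, since they cannot be read without it.

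The cost is a few sentences and a small table. The stated power becomes less favourable. No extra participants are needed.

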### **5.6 Procedure**

Recruitment strategies will include posters and brochures in hospitals and primary care centers, as well as presentations in group sessions with healthcare professionals, including those attending occupational stress consultations. Email invitations will include a brief explanation of the study and a web link to the platform. Participants will be required to submit signed informed consent electronically. Eligibility will be verified, and those meeting inclusion criteria will be formally enrolled. Participants will receive a welcome email with platform login credentials. Instructions on how to use the platform will be provided in the welcome module.

Participants will be assessed on all study variables every 8 weeks. Usability (SUS) will be assessed after completing Modules 1 and 4. Platform usage will be tracked (logins, completed modules, submitted tasks).

